1.1 SYNOPSIS

Title:	A Randomized, Double-blind, Placebo-controlled Study to Evaluate the Effects of a Dietary Supplement on Children's Health Outcomes
	This is a virtual, two-armed, randomized, double-blinded, placebo- controlled clinical trial that will last 6 months. Participants will take the NuBest Tall Growth Protein Powder or a placebo product daily.
Study Description:	The children's parents will complete questionnaires at baseline and regularly during the study period (Month 1, Month 2, Month 3, Month 4, Month 5, and Month 6).
	The children will complete cognitive assessments at home at Baseline and Month 6 (Endline).
	Parents will also provide height and weight measurements of the children at Baseline, Month 2, Month 4, and Month 6.
	Primary Objective: To examine the effect of the NuBest Tall Growth Protein Powder on cognitive function.
Objectives:	Secondary Objective: To investigate the impact of the NuBest Tall Growth Protein Powder on a range of health parameters, including height, weight, energy levels, immune function, and digestion.
	Primary Endpoint: The primary endpoint of this study is an improvement in cognitive function. Cognitive battery testing scores will be compared across the trial measurement points.
Endpoints:	Secondary Endpoints: The secondary endpoint is an increase in a range of parameters associated with health, including height, weight, energy levels, immune function, and digestion. Parents will provide height and weight measurements for the children and will complete questionnaires evaluating other health outcomes.
Study Population:	This study will recruit 60 participants (60 pairs of parents + child). The parents may be of any age group, the children must be aged as follows: Boys: 12 to 16 years Girls: 10 to 14 years
	Arm 1: Intervention - 30 participants

	Arm 2: Placebo - 30 participants		
Description of Sites/Facilities Enrolling Participants:	Virtual		
Description of Study Intervention:	 After eligibility is established, participants will complete a Baseline questionnaire, the Baseline cognitive assessment, and provide the Baseline height and weight measurements. Participants will be randomly allocated to either the intervention or placebo group. The participants and Citruslabs will not be informed who is in the test or the placebo group. Participants will begin taking their respective product for 6 months. The children will drink one scoop of the powder mixed with 6-8 oz of water, milk, or smoothies. Parents will complete questionnaires at the end of Month 1, Month 2, Month 3, Month 4, Month 5, and Month 6, and will provide further height and weight measurements at Month 2, Month 4, and Month 6. The children will repeat the cognitive assessments at Month 6 (endline). 		
Study Duration:	6 months		
Participant Duration:	6 months		
Product Instructions:	 The test products must be consumed in the morning. Combine one scoop of the powder with 6-8 oz of water, milk, or smoothies. Do not use NuBest Protein Powder for baking or cooking recipes. 		
Stadiometer Instructions:	 Step 1: Upon powering on the device, securely affix it to the wall, ensure that the height measuring instrument remains perpendicular to the ground and parallel to the wall at a 90-degree angle. Step 2: Once you've adjusted the height accordingly, press the measurement key only in the absence of any obstacles. Choose a flat ground without steps, and try to avoid testing on carpets or uneven areas with plush carpets or rugs. Ensure the device is perpendicular to the ground. 		
Compensation	\$150 Visa gift cardFitBit Smart Scale		

Ultrasonic Height Measuring Stadiometer

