3 OBJECTIVES AND ENDPOINTS

OBJECTIVES	ENDPOINTS	TIMEPOINTS	ASSESSED BY	JUSTIFICATION FOR ENDPOINTS
Primary				
To examine the effect of the NuBest Tall Growth Protein Powder cognitive function.	Improvement in score on assessments: • Double Trouble • Feature Match • Grammatical Reasoning • Digit Span • Token Search	Baseline and Month 6	Cognitive Battery Testing	The combination of these cognitive assessments will provide objective data on the efficacy of the product in improving specific domains of cognitive function.
Secondary				
	Increase in height			

	Maintenance of a healthy weight	Baseline, Month 2, Month 4, Month 6 (height & weight measurements)	Height measured using an Ultrasonic Height	
To investigate the impact of the NuBest Tall Growth Protein Powder on a range of health parameters, including height, weight, energy levels, immune function, and digestion.	Increase energy levels		Measuring Stadiometer	The combination of objective measurements and questionnaires will provide both independent and participant perception data on secondary health parameters.
	Improved signs of digestive health		Weight measured using a FitBit Smart Scale.	
	Increased immune	Baseline, Month 1, Month 2, Month 3, Month 4, Month 5, Month 6.		
	function (assessed via the number of times the child has been ill in the past 6 months)		Study-specific questionnaires	

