4.2 SCIENTIFIC RATIONALE FOR STUDY DESIGN

To best understand the actual benefits of the test product without the influence of a potential placebo effect, a randomized, placebo-controlled, double-blinded study design is the gold-standard method. A 6-month study duration provides sufficient time for the test product to provide metabolic effects that may lead to enhanced health outcomes.

The data collection intervals for this trial were chosen to minimize the participant burden while still collecting valuable data about the efficacy of the test product. In addition to subjective data collected from questionnaires, height and weight measurements using a standardized tool will provide a non-biased, independent assessment of changes in height and weight across both groups. In addition, the cognitive assessments will provide an objective measurement of changes in cognitive function.

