7 STATISTICAL CONSIDERATIONS

Following data collection and the completion of the trial, the data will be analyzed by Citruslabs to determine the effect of the intervention versus the placebo. Between-arm and participant repeated measures between time point statistical tests will be used to examine differences in health outcomes during the study and compared to the placebo. Percentages of people who experienced improvements will also be examined. The analysis will adopt an intent-to-treat (ITT) approach, reflecting the primary objective of assessing the effectiveness of the test product as it would be used in the general population, inclusive of all randomized participants, irrespective of adherence or protocol deviations.

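### A comparison with placebo is implied, but no text makes it the deciding test for the primary endpoint, and the five cognitive scores have no multiplicity rule

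*Combined protocol and SAP*

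**What the plan says.** **Endpoint.** Section 1.1 defines the primary endpoint as an improvement in cognitive function and adds: "Cognitive battery testing scores will be compared across the trial measurement points". Section 3 lists five tests (Double Trouble, Feature Match, Grammatical Reasoning, Digit Span, Token Search) under "Improvement in score on assessments", measured at Baseline and Month 6. Its justification column says that the tests in combination will give "objective data on the efficacy of the product in improving specific domains of cognitive function". It names no composite, lead score or success rule.

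**Analysis.** Section 7 is one paragraph. Its aim is "to determine the effect of the intervention versus the placebo". It continues: "Between-arm and participant repeated measures between time point statistical tests will be used", and that same sentence goes on to say that the purpose is to look at differences during the study and relative to placebo. Then: "Percentages of people who experienced improvements will also be examined". No model, significance level, definition of improvement or multiplicity procedure is given there or elsewhere.

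**Context.** Section 5.4 says that between-group comparisons will serve to assess efficacy against placebo. Section 4.2 explains the design as a way to see the benefit "without the influence of a potential placebo effect" and speaks of an "independent assessment of changes in height and weight across both groups". Section 4.3 says that the commercial dose is used partly to support marketing claims. Section 6.3 has allocation unblinded after the study ends and before the analysis.

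**The concern.** The aim and the endpoint point to different comparisons. The aim is a contrast with placebo; the endpoint sentence describes a contrast over time. In children aged 10 to 16 who take the same five tests again after six months, scores may rise through practice or maturation in both arms. A comparison over time cannot separate such a rise from a product effect. A between-arm comparison can, because gains shared by both arms cancel.

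Naming the between-arm comparison still leaves five of them. Without a rule, the plan does not say whether one significant score, two, or all five would count as success.

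Suppose the active arm improves but does not differ from placebo, or one score of five is significant. The plan cannot say whether the primary endpoint was met. The choice would then be made by analysts who know the allocation, in a study intended to support claims. Unblinding before analysis is not an error in itself, but it is the reason the rule should be written down first.

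**Working it through.** **Inputs from the documents:** 30 children per arm (Sections 1.1 and 5.4), five primary scores (Section 3), two cognitive time points (Sections 3 and 6.6).

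**Assumptions, because the text gives no values:** two-sided 0.05 per test, zero product effect, no dropout, inter-test correlation 0.2 to 0.6, pre-post correlation r from 0.5 to 0.8. Each success rule below is also assumed. The plan states no error rate, so there is no figure of its own to reproduce.

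**1. Five between-arm tests.** With independent tests, the chance of at least one significant result is 1 − 0.95^5 = 22.6%. Simulation with correlated scores at 30 per arm gives:

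| Inter-test correlation | Any of five significant | Any of five, favouring the product |
|---|---|---|
| 0.2 | 21.7% | 10.9% |
| 0.4 | 19.5% | 10.0% |
| 0.6 | 16.9% | 8.6% |

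Under other rules, over the same correlations, the rate favouring the product is about 1-2.5% if at least two scores must be significant, and below 0.1% if all five must be. The plan does not choose among these rules, so the rate could lie anywhere from below 0.1% to about 11%.

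**2. Within-arm test on one score.** This matters only if the active arm's own change is used as evidence of efficacy. For a shared gain g in SD units, the SD of change is √(2(1 − r)) and the paired t-test has noncentrality g/√(2(1 − r)) × √30.

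- g = 0.2, r = 0.5: 0.2/1.000 × 5.477 = 1.095, significant improvement in 18.4% of trials.
- g = 0.2, r = 0.8: 0.2/0.632 × 5.477 = 1.732, 38.8%.
- g = 0.5, r = 0.5: 0.5/1.000 × 5.477 = 2.739, 75.4%.
- g = 0.5, r = 0.8: 0.5/0.632 × 5.477 = 4.330, 98.7%.
- g = 0: 2.5% in the improvement direction.

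**3. After the change.** By simulation with zero effect, Holm over five ANCOVA tests gives any significant result in 3.7-5.1% of trials (1.8-2.6% favouring the product). One composite gives 4.7-5.3% (2.3-2.8%).

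**4. Cost in power.** At 80% power and 30 per arm, the two-sample t-test detects 0.736 SD at 0.05 and 0.909 SD at 0.05/5 = 0.01, Holm's first step. ANCOVA multiplies these by √(1 − r²). At r = 0.6 the factor is 0.8:

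- One test at 0.05: 0.736 × 0.8 = 0.59 SD.
- One test at 0.01: 0.909 × 0.8 = 0.73 SD.
- Composite at inter-test correlation 0.4: the SD of the mean of five z-scores is √((1 + 4 × 0.4)/5) = 0.721, so a common shift of 0.588 × 0.721 = 0.42 SD per test.

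**The case against.** The strongest reply is that the plan already settles the contrast. Section 5.4 links efficacy to between-group comparisons, Section 7 opens with the placebo comparison, and the sentence that lists the tests closes by referring to placebo again. The percentages are introduced as an addition, which reads as supplementary. This largely stands: the between-arm contrast is implied. But these are statements of intent. None attaches the contrast to the primary endpoint, and the endpoint sentence itself describes something else.

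A reader might infer from the synopsis that the active arm's own gain is enough to meet the endpoint. The documents do not say so: Sections 1.1 and 3 define what is measured, not what counts as success, and Sections 5.4 and 7 point the other way. The within-arm rates above are therefore conditional.

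A reader might also infer that the plan carries a 20% false-positive rate. That figure needs an any-one-of-five rule, which appears nowhere, and Section 3 speaks of the tests in combination. The supportable statement is that the rate is undefined.

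Finally, ANCOVA with Holm or a composite is not the only adequate choice. Another prespecified between-arm analysis with error control would also close the gap.

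**Conclusion.** The concern holds in this form: the placebo contrast is implied but not named as the deciding test, and five primary scores have no rule for combining them or controlling error. The false-positive rate of the primary conclusion is therefore undefined.

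With zero effect, 30 per arm and two-sided 0.05, it is about 17-22% in total (9-11% favouring the product) if any one unadjusted between-arm score suffices, and about 1-2.5% favouring the product if two are needed. Only if the active arm's change were taken as efficacy would a shared gain of 0.2 to 0.5 SD give significance on one given test in 18-39% to 75-99% of trials. The success rules, gains and correlations are assumptions.

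This goes beyond missing detail, because the choice decides whether an inert product could be reported as effective. It should be settled before allocation is revealed, since a rule chosen afterwards would carry little weight.

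**What to change.** Amend Sections 1.1, 3 and 7, dated before the unblinding in Section 6.3.

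- **Primary analysis:** the between-arm difference at Month 6, by ANCOVA adjusted for the baseline score, two-sided 0.05.
- **Multiplicity:** prespecify one of two options, which answer different questions. (A) The five scores with Holm adjustment, if claims about specific domains are wanted; a claim for a test needs a Holm-adjusted p below 0.05 in favour of the product. (B) One composite, the mean of the five z-scores standardised on the pooled baseline mean and SD and oriented so that higher is better, with single scores supportive.
- **Within-arm tests and percentages improved:** state that they are descriptive and cannot support an efficacy claim.
- **Height (secondary):** make the baseline-adjusted between-arm difference at Month 6 the deciding contrast, since growing children gain height in either arm.

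The cost is wording and one prespecified model; no new visits or data. Option A raises the detectable difference per test from 0.59 to 0.73 SD at Holm's first step. Option B detects a common shift of 0.42 SD but can dilute an effect confined to one test. Within-arm gains could no longer be used for claims.

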2 INTRODUCTION

2.1 STUDY RATIONALE

Protein is fundamental to growth and the repair of body tissues; hence, its adequacy in children's diets is critical for optimal physical development. Studies have highlighted the role of dietary protein in increasing height and weight in children, suggesting a direct correlation between protein intake and growth metrics¹⁻³. Similarly, essential vitamins such as Vitamin A, C, D, E, and B-complex and minerals like Calcium, Iron, and Zinc have well-documented contributions to other aspects of physical development, bone health, immune function, and cognitive development^{4,5}. For instance, Vitamin D's role in bone mineralization is well-documented⁶, while Iron and Zinc have been associated with cognitive function and immune defense⁷ Furthermore, emerging research on the gut-brain axis underscores the significance of digestive health in cognitive and immune system functions, advocating for the inclusion of probiotics and prebiotic fibers in dietary regimens for children⁸.

In the USA, many people are at risk of vitamin, mineral, and/or other micronutrient deficiencies⁹⁻¹¹. Children and adults are consuming more low-nutrient foods with added sugar and excess fats as compared to healthy, high-quality calories and micronutrients. The risk of this is further exacerbated by socioeconomic and family income to poverty ratio¹⁰. However, research has suggested that dietary supplements can be helpful in meeting nutrient requirements for some micronutrients.

With this in mind, the test product has been developed and contains a proprietary blend of vitamins, minerals, and probiotics designed to enhance children's and teenager's health outcomes through the aforementioned mechanisms. This study will assess the effects of the test product on a range of health outcomes in children over the course of 6 months.

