2.2 RISK/BENEFIT ASSESSMENT

Immediate risks:

There are no predicted risks associated with this product. However, some people may experience adverse reactions when trying a new product. NuBest Tall Protein contains milk-based ingredients, so it is not suggested for those with a dairy allergy. It does not contain soy, grain, wheat, GMO, or gluten.

As dairy can interact with a number of medications, all medications should be separated by a minimum of 4 hours from taking the test product.

Long-term risks:

There are no predicted long-term risks related to using this product. Any short-term risk should dissipate after discontinuing the test product.

Immediate benefits:

Participants may experience positive changes in overall health. Also, participants might experience increased energy levels, immune function, and overall well-being.

Long-term benefits:

Participants may experience an increase in height, maintenance of a healthy weight, and enhanced quality of life due to an increase in overall health.

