5 STUDY POPULATION

5.1 INCLUSION CRITERIA

To be eligible to participate in this study, an individual must meet all of the following criteria:

- 1. A parent of a child within the following age ranges:
 - Boy: 12 to 16 years
 - Girl: 10 to 14 years
- 2. Interested in their child trialing a dietary supplement designed to improve overall health outcomes in children, including height, maintenance of a healthy weight, cognitive function, immune function, and energy levels.
- 3. Willing to refrain from giving their child any vitamins, minerals, or herbal supplements of any kind for the duration of the study
- 4. Parents willing to weigh and measure the height of their child throughout the study
- 5. Generally healthy do not have any uncontrolled chronic disease

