6.3 RANDOMIZATION AND BLINDING

Participants will be randomized into the intervention group (NuBest Tall Growth Protein Powder) or into a placebo product control group. Randomization occurs via a randomization tool that will equally place participants into a group that will use product A or B. The research coordinator who will conduct the randomization will not know which product is the test product and which is the control.

This study will be double-blinded; the study participants and study coordinators will be blinded to the intervention or product allocation. Only the sponsor will know which product, A or B, contains the active ingredients. After the study is complete, the allocation will be unblinded prior to the analysis. Both groups will receive products that look identical.

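### The Synopsis counts an increase in weight as success while Section 3 asks for a healthy weight to be maintained, a term that is never defined; the two should be reconciled before unblinding.

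*Combined protocol and SAP*

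**What the plan says.** The Synopsis (Section 1.1) puts weight in a list of five parameters governed by one verb: "The secondary endpoint is an increase in a range of parameters associated with health, including height, weight, energy levels, immune function, and digestion".

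The endpoint table in Section 3 treats height and weight differently. Height is to increase; for weight the entry is "Maintenance of a healthy weight". Section 2.2 draws the same contrast ("Participants may experience an increase in height, maintenance of a healthy weight, and enhanced quality of life"), and inclusion criterion 2 in Section 5.1 also uses the maintenance wording ("designed to improve overall health outcomes in children, including height, maintenance of a healthy weight, cognitive function, immune function, and energy levels").

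Section 4.2 is neutral, promising an "independent assessment of changes in height and weight across both groups". The secondary objective is also non-directional.

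Section 7 plans between-arm tests and repeated-measures tests between time points, and adds: "Percentages of people who experienced improvements will also be examined". It does not say what an improvement in weight is. Sections 5.1 and 5.2 set no weight or BMI limit for entry.

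**The concern.** An increase in weight and the maintenance of a healthy weight are different endpoints, and one child can meet either without the other. The children are 10 to 16 years old and are followed for 6 months, so most should gain weight whatever they drink. An endpoint that any gain satisfies does not separate product from placebo unless it is judged between the arms. Section 7 also plans two summaries that do not rely on the placebo arm: tests between time points, and percentages improved.

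At stake is the weight claim. If nothing is settled beforehand, the report could call a within-arm gain, or a high percentage gaining weight, a favourable result. It could equally call the absence of excess gain favourable under the maintenance wording. Section 6.3 states "After the study is complete, the allocation will be unblinded prior to the analysis", so a direction left open until the analysis would be chosen with the arms known.

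**Working it through.** The documents give no figure for weight change, so there is nothing to reproduce. The check is a comparison of the text, followed by an illustration.

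**Step 1: the weight wordings side by side.**

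| Place | Favourable result for weight |
|---|---|
| 1.1 Synopsis, secondary endpoint | Increase |
| 3, endpoint table | Maintenance of a healthy level |
| 2.2, long-term benefits | Maintenance of a healthy level |
| 5.1, criterion 2 | Maintenance of a healthy level |
| 4.2, design rationale | None stated (changes) |
| 1.1 and 3, secondary objective | None stated (impact) |
| 7, analysis | None stated (improvement undefined) |

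The conflict is between the Synopsis and Section 3. The neutral entries contradict neither.

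**Step 2: do the two wordings score children alike?**
- A child above a healthy range at Baseline who gains further meets the Synopsis wording and not the Section 3 wording.
- A child within range whose weight stays stable can meet the Section 3 wording and not the Synopsis wording.
- A child within range who grows normally can meet both.

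Because entry is not restricted by weight or BMI, the first kind of child can be enrolled.

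**Step 3: what ordinary growth alone would produce.** The documents give n = 30 per arm. Assumptions, not in the documents: 6-month gain is normal with mean 2 to 3 kg and SD 1.5 to 4 kg, identical in both arms.

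- Share gaining weight = Φ(mean/SD). Lowest: Φ(2/4) = 0.691, and 30 × 0.691 = 20.7 children. Highest: Φ(3/1.5) = 0.977, and 30 × 0.977 = 29.3 children. So about 21 to 29 of 30 in each arm would gain weight with no product effect.
- Within-arm paired t-test, two-sided 5%, noncentrality = mean/(SD/√30). Mean 2, SD 4: 2/(4/5.477) = 2.74, power 0.754. Mean 2, SD 3: 3.65, power 0.942. Mean 2, SD 2: 5.48, power 0.9996. A significant within-arm gain is likely throughout the range.
- Between-arm comparison: expected difference 0, 95% half-width = t(0.975, 58) × SD × √(2/30) = 2.002 × SD × 0.2582. SD 1.5 gives 0.78 kg and SD 4 gives 2.07 kg.

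Under these assumptions the within-arm summaries look favourable in both arms, while the between-arm difference is centred on zero as it should be.

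**Step 4: how precise in-range counts would be.** Further assumptions: share in range at Baseline b = 0.65 to 0.80, share of those staying in s = 0.90 to 0.95, share of the others moving in e = 0.10 to 0.20.

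- Month 6 share in range = bs + (1 − b)e. Low: 0.65 × 0.90 + 0.35 × 0.10 = 0.62. High: 0.80 × 0.95 + 0.20 × 0.20 = 0.80.
- Unadjusted 95% half-width for the between-arm difference = 1.96 × √(2p(1 − p)/30): 0.246 at p = 0.62 and 0.202 at p = 0.80, or about 20 to 25 percentage points.
- Children per arm moving from outside to inside = 30(1 − b)e: from 30 × 0.20 × 0.10 = 0.6 to 30 × 0.35 × 0.20 = 2.1.

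In-range counts are therefore useful as description but weak as the basis for a conclusion.

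**The case against.** The strongest defence is that the Synopsis is only a summary. One verb is stretched over five parameters, and it cannot be literal for all of them, since an increase in digestion has no clear meaning. The endpoint table unpacks the list item by item and appears to separate height from weight on purpose, and Sections 2.2 and 5.1 agree with it. This stands: maintenance is the likelier intention, and a reader should not infer two equally live rival endpoints. It does not close the matter, because the maintenance endpoint has no measure, reference, range or scoring rule.

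A reader might also cite Section 2.1, on "the role of dietary protein in increasing height and weight in children", as evidence that weight gain is the aim. It is not. That sentence describes cited studies of dietary protein and needs no change.

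Unblinding before analysis, within-arm testing and undefined improvement affect every outcome, and height too rises with ordinary growth. That is correct, and those gaps are not peculiar to weight. What is peculiar to weight is that the protocol names two different favourable results.

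Finally, Section 7 says the purpose is to judge the product against placebo, and that comparison allows for ordinary growth. This also stands. It limits the harm to the within-arm and percentage summaries and to how the direction of a between-arm difference is read.

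**Conclusion.** The concern holds as an inconsistency between the Synopsis and Section 3 together with a missing definition. It should be corrected, but it does not threaten the trial. The textual finding rests on no assumption. The illustration (69% to 98% gaining weight, within-arm power from 0.754 to above 0.999) depends wholly on assumed means and SDs and shows only why within-arm weight gain is uninformative at these ages.

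Two stronger readings are not supported. A reader might infer that the weight analysis is invalid; it is not, because the between-arm weight difference can still be estimated and accounts for growth common to both arms. A reader might also infer that the sponsor intends to choose the direction after unblinding. The documents show only that the direction is not fixed beforehand. The matter affects one of several secondary endpoints, and the primary cognitive endpoint is untouched.

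**What to change.** Before unblinding:

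1. Reconcile Section 1.1 with Section 3 so that there is one weight endpoint. If Section 3 governs, remove weight from the parameters said to increase in the Synopsis.
2. Derive BMI-for-age-and-sex z-scores from the height and weight already collected, using one growth reference named in the protocol, and define healthy weight as a stated range on that reference. Confirm that date of birth and sex are recorded; the schedule of activities lists demographics at screening without itemising them.
3. In Section 7, base the weight conclusion on the between-arm difference in Month 6 BMI z-score, adjusted for Baseline, with a two-sided 95% confidence interval. Tabulate in-range status at Baseline and Month 6 by arm as descriptive support.
4. Report raw weight change by arm descriptively. Do not use within-arm gain or the percentage gaining weight as evidence of effect.

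The cost is wording in Sections 1.1, 3 and 7 and a routine derivation, with no new measurements. The sponsor gives up weight gain as a success claim, and the in-range table will be imprecise with 30 per arm (about 20 to 25 percentage points either way, unadjusted, under the assumptions above). That imprecision is why the continuous z-score should carry the conclusion.
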